### **9.6 Planned Interim Assessment**

To ensure the study is not under-powered, the primary endpoint will be monitored by the DSMB. The DSMB will be responsible for examining the interim results to ensure the observed incidence of outcome events is consistent with the planning estimates. Monitoring will specifically focus on the incidence of major stroke in the territory supplied by the treated artery or neurological death and aneurysm occlusion without significant parent artery stenosis.

After 50 subjects have been enrolled and followed for a minimum of 6 months post-procedure, an interim assessment will be performed. It is understood that monitoring off an earlier time point does not correspond with the primary endpoint. However, to derive an initial signal to ensure that the observed incidence is commensurate with the planning estimates, this time point should conservatively represent approximately 80% of events at 1 year. The conditional power will be examined to determine if an adjustment in the sample size is required to meet the primary objective of the study. An alpha level adjustment will not be necessary if the conditional power for the primary endpoint is >50%, based on the procedure proposed by Chen, DeMets and Lan (2004). Details of the procedure will be described in the DSMB Charter.

### **9.7 Analysis of the Secondary Safety Endpoints**

The rate of occurrence of major stroke in the territory supplied by the treated artery or neurological death at 30 days post-procedure due to procedural complications will be tabulated for the FAS population and presented using counts, percentages, and 2-sided 95% exact binomial confidence intervals. The rate of delayed intracerebral hemorrhage >30 days post procedure will be tabulated for the FAS population and presented using counts, percentages, and 2-sided 95% exact binomial confidence intervals.

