### Duration of Study Participation:

- Enrollment Duration: Approximately 18 months
- Follow-up: 3 years
- Total Study Duration: Approximately 54 months

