### Secondary Endpoints:

- Safety:
  - Occurrence of major stroke in the territory supplied by the treated artery or neurological death at 30 days post-procedure due to procedural complications
  - Delayed intracerebral hemorrhage >30 days post-procedure
- Effectiveness: Device deployment success rate at the target site

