## **6 ADVERSE EVENTS**

The following adverse events will be collected during the course of the study on the eCRFs.

- All Adverse Events (AE) with an underlying neurological cause (Neurological Adverse Events)
- All Device Related Adverse Events
- All Procedure Related Adverse Events
- All Serious Adverse Events (SAE's)

Adverse event status will be evaluated throughout the study. These will include new events occurring after the point of consent in the study until a subject exits the study. Subjects who are enrolled, underwent surgery to implant to study device but did not have the Pipeline™ device implanted for any reason will be followed for 30 days and relevant safety events will be collected. Investigators must obtain all information available to determine the causality and outcome of the AE and to assess whether it meets the criteria for classification as a serious and/or unexpected event requiring notification to the Sponsor, regulatory agency, and as applicable, IRB/EC, within the specified reporting timeframe. AEs will be categorized using the definitions in **Section 6.1**.

All study AEs, as well as the treatment and follow-up required, should be documented in the subject's medical records and in the eCRF. All study AEs will be followed by the Investigator until resolution or until the end of the 3-year follow-up. A list of potential anticipated adverse events is provided in **Section 10.2**.

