### 9.3 Analysis Population

The analysis population will be comprised of the results from 141 treated subjects. Results will be presented based on two populations:

*Intention to Treat* (ITT): defined as all enrolled subjects in whom deployment of the Pipeline™ device was attempted. It is possible that the Pipeline™ device may not reach the target site and the **operator** would not attempt to deploy it, in the rare event that happens, that subject will not be considered part of the ITT population.

*Full Analysis Set* (FAS): defined as a subset of ITT including only those in whom the Pipeline™ device was implanted.

*Per protocol* (PP): defined as all enrolled subjects, had the Pipeline™ device implanted, and were followed without any major protocol deviations.

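### Section 9.7 reports delayed intracerebral hemorrhage as a crude FAS proportion with no stated end of window and no allowance for incomplete follow-up

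*Combined protocol and SAP*

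**What the plan says.** The Synopsis and Section 3.2 list two secondary safety endpoints. One is fixed at 30 days. The other is "Delayed intracerebral hemorrhage >30 days post-procedure", which has a start but no end. Section 21 does not define the term further.

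Section 9.7 keeps the same lower bound: "The rate of delayed intracerebral hemorrhage >30 days post procedure will be tabulated for the FAS population". The result is to be "presented using counts, percentages, and 2-sided 95% exact binomial confidence intervals". Section 9.3 describes the FAS as "defined as a subset of ITT including only those in whom the Pipeline™ device was implanted", with no condition on being alive or in follow-up after Day 30. It also says: "The analysis population will be comprised of the results from 141 treated subjects".

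On exposure, the Synopsis gives "Enrollment Duration: Approximately 18 months" and "Follow-up: 3 years". Section 5.7.5 makes the 3-year visit the last one. Section 6 says of adverse events: "These will include new events occurring after the point of consent in the study until a subject exits the study". Section 5.11.1 allows withdrawal at any time.

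The rules for incomplete follow-up in Sections 9.1, 9.4, 9.5 and 9.10 concern the primary endpoints only. Section 9.4 adds a sensitivity analysis for primary safety that censors early withdrawals. Section 9.7 has no counterpart.

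**The concern.** The other named safety rates have a stated time: 1 year for primary safety, 30 days for the other secondary safety endpoint, and 1 year for device-related neurologic events. Delayed hemorrhage is the exception, and it is the one whose window may run to 3 years.

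Two consequences follow from a crude proportion over all implanted subjects. First, a subject who withdraws at month 8 counts the same as one observed event-free for 3 years. Hemorrhages after exit are not seen, so withdrawal can only lower the observed rate, which is the flattering direction for a safety endpoint. Second, Section 9.7 does not say when the table is produced. With entry spread over about 18 months, any tabulation before the last 3-year visit averages over unequal exposure and describes no single period. A reader could not tell whether such a figure is a 1-year risk, a 3-year risk or something between.

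**Working it through.** The documents give no expected rate for delayed hemorrhage, so there is no plan figure for this endpoint to reproduce. The 141 subjects come from Table 7, which does reproduce (52, 63, 80, 104, 141). Each entry is the smallest n whose one-sided 97.5% Clopper-Pearson upper limit is below 15%, using the fractional count n × p.

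**Inputs from the documents:** 141 treated subjects (9.3); accrual of about 18 months and follow-up of 3 years (Synopsis); window opening after Day 30 (9.7).

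**Assumptions:** constant hazard h after Day 30 of 1% per year, range 0.5% to 2%; uniform accrual; dropout by 3 years of 0%, 10%, 20% or 30%, unrelated to hemorrhage risk.

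**Step 1. Fixed-horizon risk.** Risk to day d = 1 − exp(−h(d − 30)/365).
- 3 years, h = 0.01: 1 − exp(−0.01 × 1065/365) = 2.88%.
- 1 year, h = 0.01: 1 − exp(−0.01 × 335/365) = 0.91%.

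**Step 2. Crude proportion by date of tabulation, no dropout.** Average the Step 1 formula over the 141 subjects, with follow-up capped at 1095 days. When the last subject reaches 1 year, follow-up runs from 12 to 12 + 18 = 30 months, with mean 1.75 years. Mean exposure after Day 30 is 1.75 − 30/365 = 1.668 years, and 1 − exp(−0.01668) = 1.65%.

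| Last subject has reached | h = 0.5% | h = 1% | h = 2% |
|---|---|---|---|
| 1 year | 0.83% | 1.65% | 3.28% |
| 2 years | 1.28% | 2.55% | 5.03% |
| 3 years | 1.45% | 2.88% | 5.67% |

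The effect of the tabulation date is 2.88/1.65 ≈ 1.7. At h = 1% the expected counts are about 2.3 events (141 × 1.65%) and 4.1 events (141 × 2.88%).

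**Step 3. Crude proportion after all 3-year visits, with dropout d.** Let μ = −ln(1 − d)/3 and a = 30/365. The expected observed proportion is [h/(h + μ)] × exp(−μa) × [1 − exp(−(h + μ)(3 − a))]. For h = 0.01 and d = 10%, μ = 0.0351, giving 0.2216 × 0.9971 × 0.1234 = 2.73%.

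| Dropout by 3 years | h = 0.5% | h = 1% | h = 2% |
|---|---|---|---|
| 0% | 1.45% | 2.88% | 5.67% |
| 10% | 1.37% | 2.73% | 5.37% |
| 20% | 1.29% | 2.57% | 5.07% |
| 30% | 1.21% | 2.41% | 4.75% |

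At h = 1% the relative shortfall runs from 1 − 2.73/2.88 ≈ 5% to 1 − 2.41/2.88 ≈ 16%. A Kaplan-Meier estimate targets the 0% row at every dropout level, given the same assumption of unrelated dropout.

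**Step 4. Denominator.** Suppose 5 subjects leave by Day 30 and 3 events occur. Then 3/141 = 2.13% (95% CI 0.44% to 6.09%) and 3/136 = 2.21% (0.46% to 6.31%). The difference is 0.08 percentage points.

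**The case against.** The strongest reply is that the window does have a practical end. Every treated subject is followed for a planned 3 years and events are collected until exit, so the natural reading is Day 31 to the 3-year visit. No early report of this endpoint is planned: the interim assessment in Section 9.6 concerns the two primary outcomes. On that reading staggered entry drops out, and Step 2 confirms that the crude figure at completion equals the 3-year risk when nobody leaves. This stands, and it limits the point to withdrawal plus any earlier tabulation. It does not remove the point, because the documents neither state that reading nor say when Section 9.7 is run.

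The constant hazard can also be challenged. The nearest evidence is front-loaded: Section 9.6 expects about 80% of 1-year events by 6 months, and Section 1.2.3 gives 5.6% at both 180 days and 1 year in PUFs. That evidence concerns a different composite that includes periprocedural events, but the challenge is fair. If every delayed hemorrhage fell within the first 12 months, the factor of 1.7 would become 1, and the dropout bias would shrink too.

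Four stronger readings might be inferred, and the documents support none of them.
- **A threefold distortion.** 0.91% against 2.88% compares a 1-year risk with a 3-year risk. These are different quantities and would differ just as much under the fix.
- **A rate that can never be compared with a fixed-horizon figure.** At completion it approximates the 3-year risk.
- **An invalid exact interval.** With independent subjects at unequal risks, the variance of the count is no larger than the binomial variance at the mean risk. The interval is therefore not too narrow for the mean risk on that account.
- **A material denominator error from subjects gone by Day 30.** Step 4 shows that it is negligible.

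Finally, few events are expected and all recorded data are listed (Section 9.1), so a reader of the listings could rebuild a horizon. A separate Statistical Analysis Plan, mentioned in Sections 9.1 and 9.10 but not among the documents here, may name one.

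**Conclusion.** The concern holds in a limited form. Section 9.7 names no horizon and has no rule for incomplete follow-up, and the method it does state treats partly observed subjects as fully observed. After all 3-year visits, the consequence is a downward bias of about 0.15 to 0.47 percentage points on 2.88% (2.88 − 2.73 and 2.88 − 2.41). In an earlier tabulation it is a figure of mixed exposure, up to about 1.7 times below the value at completion.

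These sizes rest on assumed hazards, a constant hazard shape and assumed dropout, since the documents give none of the three. They are small beside the sampling error: 3 events in 141 give an interval of 0.44% to 6.09%. The endpoint carries no hypothesis test, so this is a matter of interpretability and a minor improvement, not a threat to the trial's conclusions.

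**What to change.** In Section 9.7, state the horizons as Day 31 to 1 year and Day 31 to 3 years. At each, report the Kaplan-Meier cumulative incidence, or the Aalen-Johansen estimate with death as a competing event, among FAS subjects in follow-up at Day 31, censoring at study exit. Give 95% intervals and numbers at risk. Keep the planned count, percentage and exact interval alongside, and say when the table is produced.

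No new data are needed. Adverse event start dates already feed the analysis, with rules for missing ones in Section 9.11.2, and censoring at withdrawal extends what Section 9.4 already does as a sensitivity analysis for primary safety. The cost is a wording change and one extra table, whose intervals will be wide because few events are expected. If the separate Statistical Analysis Plan already fixes a horizon, Section 9.7 should refer to it.

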### **9.8 Secondary Effectiveness Endpoint**

The proportion of successful device deployments will be summarized using counts, percentages, and 2-sided 95% exact binomial confidence intervals.

### **9.9 Analysis of the Additional Data**

The device-related neurologic adverse event rate at 1 year post-procedure will be tabulated for the ITT population and presented using counts, percentages, and 2-sided 95% exact binomial confidence intervals. The mRS score at 1 year will be dichotomized ( $\geq 2$  vs.  $< 2$ ) and summarized using counts, percentages, and 2-sided 95% exact binomial confidence intervals. Aneurysm occlusion will be tabulated for the Full Analysis Set and presented using counts, percentages, and 2-sided 95% exact binomial confidence intervals. The proportion of subjects who experience recurrence and require retreatment will be summarized using counts, percentages, and 2-sided 95% exact binomial confidence intervals. Procedure time, radiation exposure (dosage and time) and number of Pipeline™ devices utilized will be summarized using descriptive statistics (N, mean, median, standard deviation, minimum and maximum value, and 95% 2-sided confidence limits).

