### 3.3 Additional Data

- Device-related neurologic adverse event rate by 1 year post-procedure
- Modified Rankin Scale (mRS) score at 1 year.
- Aneurysm occlusion at 3 years post-procedure
- Recurrence and retreatment rates at 1, 2 and 3 years post-procedure
- Procedure time
- Radiation exposure (dosage and time)
- Number of Pipeline™ devices utilized

Event-relatedness will be adjudicated by an independent CEC (**Section 8.1**).

The mRS, a validated scoring system for neurologic status after stroke, will be judged by the Investigator and/or staff.

Aneurysm occlusion status will be assessed by an imaging core lab according to the scale of Roy.

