#### **4.3.2 Exclusion Criteria**

The subject must not meet any of the following general exclusion criteria:

[figure not shown]
1. Subject has received an intracranial implant (e.g. coils) in the area of the target IA within the past 12 weeks.
2. Subarachnoid hemorrhage in the past 30 days.
3. Subject with anatomy not appropriate for endovascular treatment due to severe intracranial vessel tortuosity or stenosis determined from baseline or pre-procedure imaging, or a history of intracranial vasospasm not responsive to medical therapy.
4. Major surgery in the last 30 days.
5. History of irreversible bleeding disorder and/or subject presents with signs of active bleeding.
6. Any known contraindication to treatment with the Pipeline™ device, including:
  - a. Stent is in place in the parent artery at the target IA location
  - b. Contraindication to dual antiplatelet therapy
  - c. Relative contraindication to angiography (e.g., serum creatinine  $>2.5$  mg/dL, allergy to contrast that cannot be medically controlled).
  - d. Known severe allergy to platinum or cobalt/chromium alloys.
  - e. Evidence of active infection at the time of treatment (e.g., fever with temperature  $>38^{\circ}\text{C}$  and/or WBC  $>1.5 \cdot 10^9/\text{L}$ ).
7. The Investigator determines that the health of the subject or the validity of the study outcomes (e.g., high risk of neurologic events, worsening of clinical condition in the last 30 days) may be compromised by the subject's enrollment.
8. Pregnant or breast-feeding women or women who wish to become pregnant during the length of study participation.
9. Participating in another clinical trial during the follow-up period that could confound the treatment or outcomes of this investigation.

Before any subject is treated in the study, the baseline angiogram will be reviewed by a Pipeline™ device expert to ensure that the target IA is amenable to treatment with the Pipeline™ device.

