### **5.3 Screening and Baseline Evaluations**

Each subject will undergo a neurologic examination and assessment using the mRS and NIHSS, blood draw for hematocrit, platelet count, platelet function testing as per standard patient care (e.g. using VerifyNow (Accumetrics)), serum creatinine, and a pregnancy test (if applicable) within 60 days from the planned procedure. In female subjects, pregnancy may be ruled out by urine or blood pregnancy test, or medical history (menopause or surgical sterility). Each subject's relevant medical history and pre-existing conditions will be assessed and documented for all enrolled subjects. Current medication use within the last 30 days will be assessed and documented at baseline.

Subject eligibility assessment is to be performed based on data available to the investigator at the time of screening. This initial screening phase may include review of existing subject information (previously performed angiography, radiographs, laboratory studies, medical history, physical examination, etc.) and referral to the treating physician. Subjects must comply with all inclusion and exclusion criteria. Waivers will not be granted by the sponsor regarding subject inclusion/exclusion criteria.

If the subject meets the dimensional criteria outlined in the inclusion criteria, they should be included on the study screening log. The reason of non-eligibility for all subjects who are deemed ineligible by the Investigator should also be recorded on the study screening log. The screening log serves as a method for Covidien to ensure that there is no selection bias in the trial.

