## 9 STATISTICAL METHODS AND DATA ANALYSIS

### 9.1 General Principles

Tabulations of summary statistics, graphical presentations, and statistical analyses will be performed using SAS software version 9.2 or higher. The statistical analyses will be based on data pooled across sites in aggregate, retaining site in the statistical models that allow for the inclusion of fixed effects. All subset summary tables and data listings will be sorted by subject and site. The pre-procedure observations will be used as the baseline value for calculating post-procedural changes from baseline.

Continuous demographic parameters, such as the age of the subject at the time of enrollment, will be summarized for the ITT population using descriptive statistics (N, mean, median, standard deviation, minimum and maximum value, and 95% 2-sided confidence limits). Categorical demographic parameters, such as gender, will be summarized as a proportion of the ITT population using Clopper-Pearson 95% 2-sided confidence limits. Clinical and high risk factors will also be summarized as a proportion of the ITT population with Clopper-Pearson 95% 2-sided confidence limits.

Data obtained during the neurological examination using the Modified Rankin will be summarized at each time point using descriptive statistics.

Adverse events will be coded according to the MedDRA system dictionary. The percentage of subjects experiencing adverse events will be summarized by body system and preferred term. Subject counts will be tabulated for all adverse events for the ITT population. Adverse events will also be tabulated for events that occurred within the first 30 days of the procedure. Tabulated subject counts will be presented as a proportion of the ITT population with 95% binomial confidence intervals.

Summarizations predicated on continuous variables will be based on a generalized linear model, predicated on maximum likelihood, specifying the dependent variable as a variable with a continuous distribution. The single factor included in the model will be site. The baseline scores for specific parameters may be added to the analysis to increase the precision of the model. Probability values <0.05 will be considered significant.

Summarizations predicated on proportions will be based on a generalized linear model, predicated on maximum likelihood, specifying the dependent variable as a dichotomous variable with a binomial distribution. The single factor included in the model will be site.

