Modified Rankin Scale (mRS)	Scale for measuring general neurologic function. 0 No symptoms at all 1 No significant disability despite symptoms; able to carry out all usual duties and activities 2 Slight disability; unable to carry out all previous activities, but able to look after own affairs without assistance 3 Moderate disability; requiring some help, but able to walk without assistance 4 Moderately severe disability; unable to walk without assistance and unable to attend to own bodily needs without assistance 5 Severe disability; bedridden, incontinent and requiring constant nursing care and attention 6 Dead
Neck	Width of the opening of the aneurysm where it meets the parent vessel.
Neurological Adverse Event	An adverse event with an underlying neurological cause.
Neurological Death	Subject death due to neurologic reasons.
Per protocol (PP) population	All enrolled subjects, had the Pipeline™ device successfully implanted, and completed the study without any major protocol deviations.
Point of Enrollment	Point at which the subject signs the study Informed Consent Document.
Procedure-related Adverse Event	Event has a strong temporal relationship to the procedure (Day 0).
Procedure time	Start: Time of first Pipeline™ device introduction (i.e., once the Pipeline™ device is advanced into the microcatheter inside the blood stream of the subject.) End: Time of last Pipeline™ device delivery system removal
Retreatment	Any subsequent intervention (post procedure) performed to treat the target IA.
Screen Failure	Screened patient not enrolled in the study.
Serious Adverse Event (SAE)	An adverse event that: a) Led to death, b) Led to serious deterioration in the health of the subject, that either resulted in a. A life-threatening illness or injury, or b. A permanent impairment of a body structure or a body function, or c. In-subject or prolonged hospitalization, or d. Medical or surgical intervention to prevent life-threatening illness or injury or permanent impairment to a body structure or a body function, c) Led to fetal distress, fetal death or a congenital abnormality or birth defect (ISO 14155:2011 3.37)
Serious Adverse Device Effect (SADE)	An adverse device effect that has resulted in any of the consequences characteristic of a serious adverse event. (ISO 14155:2011 3.36)
Small Intracranial Aneurysm	< 7 mm

TERM	DEFINITION

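### The 1-year mRS is reported only as a split at 2, with no within-subject comparison to the baseline mRS that is already collected

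*Combined protocol and SAP*

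**What the plan says.** Section 3.3 lists "Modified Rankin Scale (mRS) score at 1 year" under Additional Data, below the primary and secondary endpoints. Section 9.9 gives its analysis: "The mRS score at 1 year will be dichotomized" at 2 or more versus less than 2, and "summarized using counts, percentages, and 2-sided 95% exact binomial confidence intervals". The sentence does not mention baseline.

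Baseline mRS is available. Section 5.3 requires, within 60 days before the planned procedure, that "Each subject will undergo a neurologic examination and assessment using the mRS and NIHSS", and Table 5 schedules mRS at baseline and again at 1 year.

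Section 9.1 contains two relevant general statements. It promises descriptive statistics for the mRS at each time point. It also sets a baseline rule: "The pre-procedure observations will be used as the baseline value for calculating post-procedural changes from baseline". No section then names an mRS change score, shift table or worsening proportion. Section 9.12 does specify a shift table, but for imaging parameters only.

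None of the seven inclusion or nine exclusion criteria in Section 4.3 limits baseline mRS.

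**The concern.** The cut falls at a level of disability that a subject can already have before treatment. Section 21 defines the score at the cut as "2 Slight disability; unable to carry out all previous activities, but able to look after own affairs without assistance". The exclusion for bleeding covers only "Subarachnoid hemorrhage in the past 30 days", so residual disability from an older event does not bar entry. Exclusion 7 leaves other cases to the investigator's judgment and does not rule out stable disability.

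The 1-year proportion therefore mixes subjects who arrived at mRS 2 or more with those who reached it after the procedure. It is also blind to change on either side of the cut. At stake is how this one proportion can be interpreted. The mRS is the only functional-disability scale in the schedule, and it could show losses of function smaller than the NIHSS rise of 4 or more that defines major stroke.

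**Working it through.** **Inputs from the document.** N = 141 treated subjects (Sections 9.2 and 9.3); cut at mRS 2 and a 2-sided 95% exact binomial interval (Section 9.9).

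**Inputs assumed.** The document gives neither the proportion entering at mRS 2 or more (range used: 0% to 10%) nor the proportion moving from below 2 to 2 or more by 1 year (2% and 5% used).

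**The plan's own figure.** No figure is stated for mRS, and 141 serves only as the denominator. It does reproduce. At an observed incidence of 9%, x = 0.09 × 141 = 12.69, and the 1-sided 97.5% Clopper-Pearson upper bound is 0.1499, just under 0.15. With fractional x allowed, 141 is the smallest n that achieves this, and the other four rows of Table 7 (52, 63, 80, 104) also match.

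**Formula.** Let B be the number entering at mRS 2 or more, I the number of those who fall below 2 by 1 year, and W the number who newly reach 2 or more. Assume that all 141 have a 1-year score.

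- Planned count = B − I + W
- Newly at 2 or more = W
- Difference = B − I, which is largest, at B, when nobody improves (I = 0)

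**Results with I = 0.** B = 0.05 × 141 ≈ 7 or 0.10 × 141 ≈ 14. W = 0.02 × 141 ≈ 3 or 0.05 × 141 ≈ 7.

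| B | W | Planned proportion (95% CI) | Newly ≥2, of 141 (95% CI) | Newly ≥2, of those <2 at entry |
|---|---|---|---|---|
| 0 | 7 | 7/141 = 5.0% (2.0–10.0) | 5.0% (2.0–10.0) | 7/141 = 5.0% |
| 7 | 3 | 10/141 = 7.1% (3.5–12.7) | 2.1% (0.4–6.1) | 3/134 = 2.2% |
| 7 | 7 | 14/141 = 9.9% (5.5–16.1) | 5.0% (2.0–10.0) | 7/134 = 5.2% |
| 14 | 3 | 17/141 = 12.1% (7.2–18.6) | 2.1% (0.4–6.1) | 3/127 = 2.4% |
| 14 | 7 | 21/141 = 14.9% (9.5–21.9) | 5.0% (2.0–10.0) | 7/127 = 5.5% |

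In the third row, 7 of the 14 subjects counted (50%) were already at 2 or more on entry; in the last row, 14 of 21 (67%).

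**Do the Section 9.1 summaries fill the gap?** Only in part. They are separate distributions at each visit. Suppose seven subjects go from 1 to 2 and seven others go from 2 to 1. The two distributions are then identical, the split is unchanged, and seven worsenings cannot be seen. A move from 0 to 1 or from 2 to 4 does not alter the split at all; the visit summaries may shift, but they do not show whose score changed.

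**The case against.** Several stronger readings are tempting, and the document does not support them.

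- *That the plan ignores baseline mRS.* It does not. Section 9.1 summarizes mRS at each time point, and baseline is one of them. A reader will see how many entered at 2 or more and can set that against the 1-year figure.
- *That stable disability is scored as treatment failure.* Section 9.9 never labels mRS 2 or more a poor outcome and defines no change measure. It reports status at 1 year, which is what Section 3.3 lists.
- *That baseline is the only reference in a single-arm study.* The study design part of Section 1.2.4 plans a comparison with historical stent-assisted coiling results. Baseline is the only internal reference, not the only one.
- *That the study cannot detect worsening.* Major stroke is defined by a rise in NIHSS (Section 3.1). Sudden worsening of 3 or more NIHSS points goes to the clinical events committee (Section 8.1). Neurological adverse events are collected from consent (Section 6), and analyzed events must have begun or worsened after enrollment (Section 9.11). The limitation belongs to this one mRS proportion.
- *That the inflation is known to be material.* The aneurysms are unruptured, Section 1.2.1 says most are asymptomatic until rupture, and Exclusion 7 gives the investigator discretion. The true proportion entering at 2 or more could be close to zero.

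All of this stands, and it limits the point. What it does not supply is a within-subject mRS result. The general baseline rule in Section 9.1 says which value to use if a change is calculated, but no section calculates one for mRS. The option to add baseline scores to a model is discretionary, names no parameter, and sits in the paragraph on continuous variables.

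**Conclusion.** The point holds as a minor gap in reporting. The only dedicated 1-year mRS analysis is a split at 2 without reference to the subject's own baseline, and the aggregate summaries elsewhere cannot show who got worse.

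The inflation runs from zero, if nobody enters at mRS 2 or more, to about 7 to 14 of 141 subjects (5 to 10 percentage points) if 5% to 10% do. That upper range rests on three assumptions: the entry proportion, no improvement among those subjects, and a 1-year score for all 141. The failure to show worsening within a category does not depend on the entry proportion.

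Neither primary conclusion changes, because mRS has no hypothesis, threshold or decision rule.

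**What to change.** In Section 9.9, keep the planned split and add:

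1. a shift table of baseline mRS by 1-year mRS, with deaths scored 6 as on the Section 21 scale;
2. the proportion whose mRS worsens from baseline, with an exact 95% interval;
3. the proportion newly at mRS 2 or more among those below 2 at baseline, with an exact 95% interval.

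The same sentence should name the analysis population and say how missing 1-year scores are shown, since Section 9.9 states neither for mRS.

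The cost is one extra table from data already collected, with no new visits and no change in sample size. There is one drawback. The score is judged by the investigator or site staff, so any-worsening will include some one-point rating variation. Item 3, which requires crossing the cut, gives a second view beside it. The addition is best made before the 1-year results are seen.
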